- i) Approval letters from all the IRB of record for all participating sites (or indicate that they are pending and provide upon receipt): UCLA IRB approved this study on 13 JAN 2014. UCLA IRB# 13-001670
- j) Confirm that the PI at GLA will maintain documentation of all correspondence between participating sites and their IRBs of record:

The Principal Investigator for both UCLA and VA GLA, [name], will maintain documentation of all correspondence between participating sites and their IRBs of record for UCLA, VA GLA and the Department of Defense/USAMRAA.

10. Subject Population

We plan to enroll a total of 74 subjects for this study. We will identify the 74 subjects from the VA GLA Healthcare System who are currently in treatment and have received treatment-asusual (TAU) for the last 3 months in the PTSD Clinic or the Domiciliary Care Program. TAU may consist of medication and/or group psychotherapy. In addition to TAU, Veterans who have begun a structured, evidence-based therapy such as cognitive behavior therapy (CBT), cognitive processing therapy (CPT), or Prolonged Exposure (PE) therapy at least 6 weeks prior to beginning the study, and who continue to receive therapy, may also be eligible. Subjects will be enrolled into an eight-week treatment protocol in which they will be assigned to one of two treatment groups: 1) active TNS plus TAU; or 2) sham TNS plus TAU. Study activities will be performed at the VA GLA and the Semel Institute at the University of California, Los Angeles.

Participants will be recruited as described below from the PTSD Clinic ([name], LCSW, Director) and the Domiciliary Care Program ([name]., Director) of the VA GLA Healthcare System.

PTSD Clinic:

The PTSD Clinic caseload includes over 1,800 veterans with PTSD, including approximately 400 veterans from Iraq or Afghanistan (OIF/OEF/OND). The clinic receives an average of 25 referrals a week

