Potential participants will be recruited from the VA GLA PTSD Clinic and the Domiciliary Care Program. Drs. [name] and [name], co-investigators on this study, are the primary attending physicians in the PTSD clinic, and will coordinate efforts with the clinic staff to refer patients to the study. Directors of the recruiting VA GLA programs will coordinate efforts with the staff to refer potential subjects to the study. The study will be explained to all PTSD Clinic and Domiciliary Care Program staff who will be asked to mention the study and provide potentially eligible veterans with a study brochure. The brochure will explain in lay language the goals of the study, the procedures and time commitment, and that compensation will be provided. Simple one-page flyers also will be prepared that can be left in the clinic waiting room. These will contain a brief lay language summary of the study and the telephone number for research staff to call for further information. The brochure and flyer will not be coercive or offer any undue inducements for participation, and will be approved by the IRB prior to distribution.

Inclusion criteria: In order to be included in the study, subjects must:

- 1) 21-65 years old and be a patient in the PTSD Clinic or the Domiciliary Care Program at the VA GLA;
- 2) have experienced trauma while serving in a war zone in the following U.S.Military conflicts; Multinational Force in Lebanon (1982-1984) Invasion of Grenada (1983) Invasion of Panama (1989-1990)

Gulf War (1990-1991)

Iraqi No-Fly Zone (1991-2003)

Somali Civil War (1992-1995) Intervention in Haiti (1994-1995) Bosnian War (1994-1995) Kosovo War (1998-1999) War in Afghanistan (2001-present) Iraq War (2003-2011)

- 3) meet DSM-V criteria for current warzone-related PTSD with a duration of at least 3 months:
- 4) currently receiving treament as usual (TAU) and have received TAU treatment for the last 3 months, and *may* be receiving structured, evidence-based therapy such as Prolonged Exposure therapy (PE), Cognitive Processing Therapy (CPT), or Cognitive Behavior Therapy (CBT), so long as the therapy was not initiated within 6 weeks of beginning the TNS protocol;
- 5) significant residual PTSD symptoms as evidenced by a CAPS-5 (Clinician-administered PTSD scale) score ≥ 50;
- 5) consent to be randomized to active or sham TNS treatment;

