- 6) if receiving medication for depression, anxiety, sleep, or mood stabilization, must have been on stable dose for at least six weeks prior to randomization.

We have minimized exclusion criteria in order to support inferences applicable to as broad a mix of patients presenting with PTSD as practicable. In order to avoid confounds that might make it impossible to interpret findings from the study due to a lack of exchangeability of experimental subjects, we will not include patients who exhibit:

Exclusion Criteria:

- 1) current substance abuse disorder not in remission for at least 3 months;
- 2) a history of bipolar, schizophrenia, other psychotic disorder, or dementia;
- 3) current suicidal or homicidal ideation requiring hospitalization, or suicide attempt within six months;
- 4) report of severe TBI with coma duration (30 minutes or more) at time of screening interview and/or duration of post-traumatic amnesia (1hour or greater) on the Post-traumatic Amnesia Questionnaire (PTAQ);
- 5) reported use (by patient or clinic staff) of antidepressant, antianxiety, antipsychotic, or moodstabilizer medication where the dose has not been stable for a minimum of six weeks prior to entering the randomization;
- 6) reported participation (by patient or clinic staff) in psychosocial or medication treatment through a clinic or facility other than the VA GLA PTSD Clinic or the Domiciliary Care Program;
- 7) infection or loss of integrity of skin over the forehead, where the electrode pads will be placed.

We will exclude participants who are receiving treatment for PTSD *outside* of the VA GLA PTSD Clinic or Domiciliary Care Program because such treatment may deviate from accepted treatment as usual (TAU), and the details of such treatment may not be available to the investigators. We will not exclude participants who are currently in TAU for PTSD at the VA GLA with the exception of the initiation of or change in medication status (i.e., starting or changing dose) occurring within the prior six weeks. Subjects, as well as staff providing treatment, will be informed that TAU may not change during the eight week blinded study period if the subject wishes to remain enrolled in the study. If a change in TAU is indicated based upon the subject's clinical situation, the subject will be withdrawn from the study and the clinic staff so

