informed. This exclusion is designed to reduce the confounding effects of changes in concomitant treatment with those of TNS. Because of the relative stability of this patient population after 3 months of TAU, we anticipate that this exclusion will affect only a small number of patients. Although a blanket exclusion of subjects receiving medication would avoid certain complexities in the assessment of TNS efficacy, given the frequency with which these medications are prescribed, excluding such individuals could be expected to negatively affect not only recruitment success but also generalizability.

We have chosen not to exclude subjects who may be initiating naturalistic psychosocial treatment through the PTSD Clinic or the Domiciliary Care Program. There are a number of outpatient group treatments available including:

OEF/OIF group - Operation Enduring Freedom (OEF) and Operation Iraqi Freedom (OIF) combat Veterans, discussions of issues pertaining to readjustment hack to civilian life;

Combat Trauma group - 12-week class discussion of issues related to combat trauma;

PTSD/Substance Abuse group - helps veterans remain safe in their behavior and manage emotions;

Grief Group - helps veteran who have experienced losses;

Anger Management - a 12-week program that teaches understanding of anger and coping skills;

Emotional Management - 12-week program teaches how to negotiate emotionally charged situations;

Strategies for Living – 12-week program that teaches how to more effectively use cogntive resources.

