We are allowing these treatments for two reasons. First, the subjects in this study will be significantly symptomatic, and it could be impractical or unsafe, and correspondingly unethical, to deny them access to some type of psychosocial intervention for their ongoing symptoms. Second, all subjects will be receiving TAU which may include a combination of treatments including medications, breathing exercises, and talk therapy. While a course of another psychosocial treatment through the PTSD Clinic or the Domiciliary Care Program may provide valuable support and some symptomatic relief, we believe that it is unlikely that one of these treatments would result in a significant magnitude of symptom reduction that would confound the study results. We will require that all non-study treatments be provided through the VA GLA PTSD Clinic or Domiciliary Care Program which will make it possible for us to carefully record any non-study medication or psychosocial treatments that the subjects are receiving for their PTSD. We will use uncontrolled treatment as a covariate in analyses if indicated due to unbalanced frequency or intensity of treatments received between the active and sham TNS groups.

Individuals with Major Depressive Disorder (MDD) will not be excluded if they meet the inclusion and exclusion criteria. MDD often is comorbid with PTSD, so that excluding these

subjects would limit generalizability of results. Individuals with active substance dependence, bipolar or other psychotic disorders, or severe TBI will be excluded because TNS may not work in the same manner or achieve the same degree of effectiveness in such individuals compared with patients who do not have these conditions. In this initial blinded efficacy study, we believe that it is important to eliminate these potential confounds. We do not anticipate that many subjects will be excluded because of bipolar or psychotic disorders because such patients generally have been identified prior to their registration in the PTSD Clinic or Domiciliary Care Program and are being treated elsewhere in the VA GLA. Some patients will have suffered or will suffer from an active substance use disorder, and these subjects will be excluded from the study.

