Subjects will be followed weekly with ratings of PTSD symptoms, mood and anxiety, as well as examinations for risk of suicidality. Week 8 endpoint measures will include severity and frequency of PTSD symptoms, quality of sleep, and quality of life measures. The primary endpoint measure is the change in symptom severity at the week 8 visit. The week 8 time point will be used to compare changes in symptoms between subjects who were randomly assigned to the active vs. sham TNS treatment condition. Subjects also will be interviewed an additional 4 weeks after the conclusion of the sham controlled treatment, and their mood and anxiety symptoms assessed, to examine the durability of any symptom change that subjects experienced during the initial 8 weeks. At the end of week 8, subject improvement will be assessed and those showing a $\geq 25\%$ improvement from baseline at the end of 8 weeks of treatment will be eligible to participate in the 42-month extension phase to monitor and observe possible benefits of prolonged TNS in responders. Subjects who participate in the extension phase will remain blinded. Subjects complete the PCL-M and BDI monthly during their participation in the extension phase. The PCL-M monthly score determines on-going inclusion in this phase. Subjects will be withdrawn in the case of adverse events, or symptom worsening (quantified as > 25%worsening in symptoms after one month as compared to the beginning of the extension phase as assessed using the PCL-M total score). Subjects way also voluntarily withdraw from the extension phase at any time.

Subjects who do not participate in the extension phase will be unblinded and told whether they received the active or sham-controlled treatment after all study and follow-up visits have been completed. This includes completion of the eight-week double-blind treatment phase and four-week follow-up phase for a total of 12 weeks in this study. Data will be examined for differences

between active and sham treatment, as well as safety and acceptability of the treatment. If positive, this preliminary study will serve as the basis for a larger pivotal trial of effectiveness.

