Following the baseline assessment, subjects then will be randomized to one of the two treatment conditions. Treatment assignment will be randomized within cells defined by gender, symptom severity, and presence of current medication treatment to provide a degree of balance on key underlying characteristics that otherwise would have the potential to confound the interpretation of study findings. Specifically, there will be eight strata for randomization defined by the 2 x 2 x 2 combinations of gender (male or female), symptom severity (lower or higher defined by whether the CAPS-5 score on entry is less than 78, the median value for this sample, versus being 78 or greater), and presence of current medication treatment (yes or no). Within these strata, randomization will occur in blocks of two, so that after every two patients with a given combination of stratum-defining characteristics, there will be one patient assigned to the active intervention and one to the control arm. The randomization will be carried out by associating strata with rows of the random-number table in Cochran (1977, p. 19). For the first member of each successive pair of patients presenting with a given set of stratum-defining characteristics, if the next number in the row is in the range of 5 through 9, then the patient will be assigned the active intervention, else the patient will be assigned to the sham. If the first subject was assigned the active intervention, then the next subject would be assigned the sham, and vice versa; for the next subject after that, the random-number table will be used in the same way. The pairing in the design could be considered in the analysis, and we will plan to do so using a permutation-test approach for purposes of being complete. The core motivation for the pairing, however, is to ensure that treatment assignment remains balanced across arms rather than because we believe that there is anything scientifically important about whether the subject arrives at an odd or an even number in the sequence. For our primary analysis, we will use a randomized-block ANOVA that accounts for the 2 x 2 x 2 stratification in the design but does not reduce the error degrees of freedom on account of the pairing.

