Following randomization, subjects will be scheduled to come back for a second visit when they will be given a pre-programmed stimulator, a supply of electrodes, and instructions on how to apply the electrodes and use the device. No more than one week will elapse between the first and second baseline visits. Baseline measures will not be repeated at the second baseline visit except for the CAPS-5, PCL-5, and BDI measures, which will be repeated in order to have PTSD, anxiety, and depression severity measures immediately prior to the start of treatment. Subjects will return to UCLA or the VA GLA for weekly visits and will undergo assessment of symptoms with instruments as specified in Table 1 above. The research coordinator will assess compliance, ensure that the device continues to be in good working order and that the subject has a sufficient supply of electrodes, and encourage continued compliance. In addition, the research coordinator will assess the subject for safety, inquiring specifically about any suicidal ideation and evaluate the results of scheduled assessments. If the research coordinator has any concerns about subject safety, she will immediately contact a study physician who will interview the subject and perform an independent assessment. Subjects will be removed from the study and hospitalized for any safety concerns per the procedure in the Human Subjects section.

At the conclusion of the main study (week 8 visit or sooner if the subject drops out or is removed from the study), subject improvement will be assessed and those showing a \geq 25% improvement from baseline at the end of 8 weeks of treatment will be eligible to participate in the 42-month extension phase to monitor and observe possible benefits of prolonged TNS in responders. Subjects who participate in the extension phase will remain blinded and will be asked to complete the Beck Depression Inventory(BDI) and the PTSD checklist during a monthly phone visit. Subjects who do not participate in the extension phase will be unblinded and told whether they

received the active or sham-controlled treatment after all study and follow-up visits have been completed. The device will be collected from the subject and the subject will be continue treatment in the PTSD Clinic or the Domiciliary Care Program. A summary of the results for each subject in the study will be provided to the clinic staff with the subject's permission.

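### Subjects whose usual treatment must change leave the study with no stated week-8 follow-up, and treatment started after randomization may become a covariate; either can bias the active-sham comparison

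*Combined protocol and SAP*

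**What the plan says.** **Withdrawal.** Section 12 (Exclusion Criteria) requires usual treatment (TAU) to stay fixed during the eight blinded weeks, and then states: "If a change in TAU is indicated based upon the subject's clinical situation, the subject will be withdrawn from the study". The stated purpose is to keep changes in other treatment from being confounded with TNS. The investigators expect few such cases but give no rate.

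**Endpoint and analysis.** Section 13 (Overview): "The primary endpoint measure is the change in symptom severity at the week 8 visit". Section 13 (Conduct of the study): "For our primary analysis, we will use a randomized-block ANOVA that accounts for the 2 x 2 x 2 stratification in the design". No analysis set or missing-data rule accompanies the model.

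**Data from leavers.** Section 13 (Conduct of the study) places the end-of-study assessment at the "week 8 visit or sooner if the subject drops out or is removed from the study". Table 1 has CAPS-5 at weeks 0, 4 and 8 and the PCL weekly. Section 11 provides a clinical check of withdrawn subjects as needed. A further contact four weeks after the week-8 endpoint covers all subjects outside the extension and does not name withdrawn subjects.

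**Other treatment.** Section 12: "We have chosen not to exclude subjects who may be initiating naturalistic psychosocial treatment through the PTSD Clinic or the Domiciliary Care Program". The same section adds: "We will use uncontrolled treatment as a covariate in analyses if indicated due to unbalanced frequency or intensity of treatments received". Section 10 defines usual treatment broadly: "TAU may consist of medication and/or group psychotherapy". The inclusion criteria admit subjects in PE, CPT or CBT "so long as the therapy was not initiated within 6 weeks of beginning the TNS protocol". The risk-management text also lets subjects take part in groups or psychotherapies while in the study.

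**The concern.** The withdrawal trigger is the subject's clinical state, which is close to the outcome itself. If active TNS works, more sham subjects should deteriorate enough to need a treatment change. If they are then not measured at week 8, the worst sham outcomes disappear and the arms look more alike than they are. The rule replaces confounding by changed treatment with missing data that depend on the outcome.

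The covariate rule has a related weakness. Therapy begun after randomization may be a consequence of the assigned arm, and the trigger for adjusting is an observed imbalance between arms. Conditioning on such a variable can remove part of the treatment effect, and deciding to adjust after seeing the imbalance makes the model data-driven. The primary ANOVA does not list this covariate, so whether it can enter the primary result is left open.

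The trigger is also unclear at one point. Group psychotherapy counts as usual treatment in Section 10, usual treatment may not change, and yet joining a clinic group is permitted. The text can be read as meaning medication changes only. It does not say what happens to a subject who starts PE, CPT or CBT during the eight weeks.

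**Working it through.** **Inputs from the protocol.** 74 subjects, 37 per arm (37 + 37 = 74). The available text gives no alpha, power, effect size, SD or dropout rate, so the sample size cannot be reproduced and everything below is illustrative.

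**Assumptions.** Outcome in SD units, negative favouring active. Two-sided alpha 0.05. SE of the difference = sqrt(2/37) = 0.23. True effect -0.66, which gives 80% power at 37 per arm. The week-4 effect is half of this, -0.33. The correlation r between the week-4 score and the week-8 outcome is 0.6 or 0.8. A subject is withdrawn when the week-4 score exceeds c = 1.64, 1.28 or 1.04 SD.

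**Who leaves.** Sham: 1 - Phi(c). Active: 1 - Phi(a), with a = c + 0.33.

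| c | Sham | Active | People of 37 (sham, active) |
|---|---|---|---|
| 1.64 | 5.0% | 2.4% | 1.9, 0.9 |
| 1.28 | 10.0% | 5.4% | 3.7, 2.0 |
| 1.04 | 14.9% | 8.5% | 5.5, 3.2 |

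**Route 1: completers only.** Expected estimate = -0.66 + r × [phi(c)/Phi(c) - phi(a)/Phi(a)].

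- c = 1.64: 0.1095 - 0.0587 = 0.051, giving -0.630 (r = 0.6) and -0.619 (r = 0.8)
- c = 1.28: 0.1954 - 0.1153 = 0.080, giving -0.612 and -0.596
- c = 1.04: 0.2730 - 0.1706 = 0.102, giving -0.599 and -0.578

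Simulation with 20,000 runs per setting agrees: -0.630, -0.609, -0.598 (power 77.0, 73.7, 71.2%) for r = 0.6, and -0.618, -0.595, -0.578 (power 77.8, 74.9, 72.9%) for r = 0.8. The estimate is 0.03-0.08 SD too small.

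**Route 2: exit rating carried to week 8.** Expected estimate = -0.66 + 0.33 × [1 - Phi(a)] - (1 - r) × [phi(c) - phi(a)], which runs from -0.671 to -0.647. Simulation: -0.672 to -0.646, power 73-77%. There is little bias here, because two opposing errors nearly cancel under these inputs, but power still falls.

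**Route 3: everyone followed, and a treatment change improves outcome by 0.3 or 0.5 SD.** Expected estimate = -0.66 + rescue × (sham rate - active rate).

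- Smallest change: -0.66 + 0.3 × (0.0505 - 0.0244) = -0.652
- Largest change: -0.66 + 0.5 × (0.1492 - 0.0853) = -0.628

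Simulation: -0.653 to -0.627, power 79-82%.

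**Covariate rule.** 8,000 runs, r = 0.8. Uptake is logistic in the week-4 score (intercept -1; slope 0, 1 or 2), about 30-35% sham against 25-27% active where it follows symptoms. With inert therapy the unadjusted estimate is -0.66:

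| Slope | Adjusted if arms differ by 15 points | Always adjusted |
|---|---|---|
| 0 | -0.658 | -0.658 |
| 1 | -0.636 | -0.621 |
| 2 | -0.603 | -0.574 |

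Across all settings with symptom-driven uptake, including a 0.2 SD therapy effect, the shift is 0.02-0.06 SD (conditional) or 0.03-0.09 SD (always), and power drops 2-4 points. With slope 0 there is no shift. A harsher model, with uptake set by a symptom threshold and 20-40% sham uptake, takes a true 0.50 SD to 0.36-0.40 when always adjusted, so the size depends heavily on the uptake model.

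**No true effect.** With one rule for both arms, the mean shift is below 0.01 SD and type I error is 3.7-5.2% on every route. This depends on the blind. If the active-arm withdrawal threshold were 0.3-0.5 SD lower, completer analysis would show a false benefit of 0.05-0.17 SD.

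**The case against.** - **Small and conservative.** The completer shift is 0.03-0.08 SD against an SE of 0.23, it runs toward no effect, and this is a preliminary trial expecting few such withdrawals. This stands, and it limits the severity.
- **No completer analysis is specified.** An assessment at removal is planned, and carrying it forward leaves little bias. True, but the plan does not choose that route either, and it also loses power.
- **Much of the power loss is lost numbers.** Random loss leaving 35/36, 33/35 or 31/34 subjects (sham/active) gives 78, 76 and 74%. Selection therefore adds roughly 0.5-3 points. The sharp cut-off is also the strongest symptom dependence for a given rate, full retention after a TAU change is optimistic, and the model omits the severity stratum. These points stand. Following leavers would still recover numbers as well as reduce selection.
- **The later contact may include withdrawn subjects.** Read literally it could, but it falls at about week 12 and cannot supply the week-8 endpoint.
- **Withdrawal is a deliberate choice.** The aim is TNS under fixed usual treatment. That question is legitimate, but ending measurement does not answer it without assumptions about the missing outcomes.
- **The covariate rule is conditional and may concern therapy already under way.** Adjusting for therapy status at randomization is sound. The wording does not restrict the rule to that, and new treatments may start on study.
- **The trigger is mostly clear.** Agreed for medication and clinic groups. Only a mid-study start of PE, CPT or CBT remains open.
- **Some pages are not in the public text.** Statements about what is absent apply only to the text available.

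**Conclusion.** The concern holds. A randomized subject who needs a treatment change leaves with no stated week-8 measurement and no rule for the data already collected, and the covariate rule can admit a consequence of treatment into the efficacy model.

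Under the assumed rates the withdrawal rule costs 0.03-0.08 SD of a 0.66 SD effect in a completer analysis, and roughly 2-9 points of power from 80%. The covariate rule costs 0.02-0.09 SD if uptake follows symptoms, and nothing if it does not. The usual direction is to understate a real benefit. Type I error is protected if the blind holds and both arms face the same threshold for a treatment change.

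The reading of the text is firm. The size is only moderately certain, because the protocol gives no withdrawal or uptake rates. This should be fixed, but it does not by itself invalidate the trial.

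**What to change.** 1. Define a TAU change: a medication change counts and joining a clinic group does not. State which applies to starting PE, CPT or CBT.
2. Leave device decisions to the clinicians, but separate stopping the device or changing TAU from leaving the study.
3. Collect CAPS-5 and PCL at the scheduled weeks 4 and 8 from every randomized subject who has not withdrawn consent, and analyse all as randomized.
4. Remove post-randomization treatment from the efficacy model. Allow it at most in a labelled sensitivity analysis, and report its uptake by arm. Therapy status at randomization may be a covariate if pre-specified.

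**Cost.** Protocol wording, plus visits already in Table 1. The estimate then includes the effect of any added treatment rather than TNS under fixed usual treatment. With a 0.3-0.5 SD rescue effect that moves it by 0.01-0.03 SD, less than the 0.03-0.08 SD completer shift.
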